## SYNOPSIS

Name of Sponsor/Company:	Seattle Genetics, Inc.			
Name of Finished Product:	Brentuximab vedotin			
Name of Active Ingredient:	Brentuximab vedotin			
Title of Study:	A Multi-center, Randomized, Double-blinded, Placebo-controlled, Multiple-ascending-dose Study of Brentuximab Vedotin in Adults With Active Systemic Lupus Erythematosus			
Protocol No:	SGN35-022			
Investigators:	Multicenter			
Study center(s):	Approximately 20 sites in the United States			
Study duration: The duration of treatment for each subject is 12 weeks. The overall duration of the study for each subject is up to 22 weeks, including the screening and follow-up periods.	Phase: 2a			
Objectives:				
Primary: to evaluate the safety and tolerability of brentuximab vedotin in adults with active systemic lupus erythematosus (SLE).				
Secondary: to explore the pharmacokinetics (PK) and pharmacodynamics (PD) of brentuximab vedotin and to explore the efficacy of brentuximab vedotin in adults with active SLE.				
Methodology:				
This is a multicenter, randomized, placebo-controlled, double-blind, multiple-ascending-dose study to evaluate the safety and tolerability of brentuximab vedotin in subjects with active SLE. Approximately 40 subjects in 4 dosing cohorts (10 subjects per cohort) are planned at approximately 20 study sites in the United States. Subjects will be randomly assigned in a 4:1 ratio within each dosing cohort to receive intravenous (IV) brentuximab vedotin or placebo every 3 weeks for a total of 4 doses. The doses planned for each ascending dose cohort include 0.3, 0.6, 1.2, and 1.8 mg/kg.				

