### **5.3 Method of Assigning Subjects to Treatment Group**

Once the subject meets inclusion and exclusion criteria and has provided written informed consent, the study site will request the study medication assignment using the Interactive Web Response System (IWRS).

A total of 10 subjects in each dose cohort will be randomly assigned in a 4:1 ratio, resulting in 8 subjects assigned to each of the 4 brentuximab vedotin dose cohorts and a total of 8 subjects assigned to placebo (2 per cohort).

To randomly assign a subject to treatment, the study site will use the internet to access the IWRS. Subjects will be assigned their 6-digit subject number, starting with a 3-digit site number followed by a hyphen and a 3-digit sequential number (eg, 101-001). The IWRS will provide the study drug kit number(s) of the blinded study drug to be dispensed.

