3. STUDY DESIGN

3.1. GENERAL DESCRIPTION

This is a multicenter, randomized, placebo-controlled, double-blind, multiple-ascending-dose study to evaluate the safety and tolerability of brentuximab vedotin in subjects with active SLE. Approximately 40 subjects in 4 dosing cohorts (10 subjects per cohort) are planned for study participation at approximately 20 study sites in the US. Subjects who meet inclusion and exclusion criteria will be randomly assigned in a 4:1 ratio within each dosing cohort to receive IV brentuximab vedotin or placebo every 3 weeks (Days 1, 22, 43, and 64) for a total of 4 doses. The following doses are planned for each ascending dose cohort:

- 0.3 mg/kg IV every 3 weeks for 4 doses;
- 0.6 mg/kg IV every 3 weeks for 4 doses;

Document: SGN35-022 SAP v1 V0.3
Author: [REDACTED]

Version Number: 1.0
Version Date: 31Jan2017

Template No: CS_TP_BS016 – Revision 3
Effective Date: 01Apr2016

Reference: CS_WI_BS005

[REDACTED]

- 1.2 mg/kg IV every 3 weeks for 4 doses; and
- 1.8 mg/kg IV every 3 weeks for 4 doses.

Individual doses are based on subject weight and will be administered as an IV infusion over approximately 30 minutes. Dose and/or schedule adjustments are not permitted. In-line filters are permitted. However the study drug cannot be mixed with other medications. Further instructions on the dose preparation and administration will be provided in the Pharmacy Manual.

Initiation of enrollment at the next dose level will only commence upon endorsement of the SMC following review of the safety data. Depending on the findings, the SMC may recommend additional enrollment of subjects at specific dose levels to better characterize the safety of a particular dose, or may recommend different dose regimens based on the emerging safety data. When available from each full cohort, the SMC will review all Day 85 safety data and may recommend that an already enrolled succeeding dose cohort be discontinued, or its treatment regimen truncated. Doses are not to exceed 1.8 mg/kg IV every 3 weeks or equivalent. Up to 20 subjects total may be enrolled via additional SMC-recommended cohorts for a total of up to 60 subjects.

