15.2.1.2. ANALYSIS

The following analyses will be performed for all study days with Day 85 specified as the secondary endpoint, and all other visits falling under exploratory analyses.

The percentage of subjects demonstrating SRI Response will be presented by treatment with 95% CI using Wilson's score method (SAS PROC FREQ syntax: table response/binomial (wilson)). Comparisons between each active treatment group and placebo will be performed using Fisher's exact test (two-sided). The ratio of percentages (relative risk) for active to placebo will be presented for each dose level with corresponding 95% CI, based on the score method [Farrington] (SAS PROC FREQ syntax: table trta*response / relrisk(method=score equal)). Percentages with Wilson 95% CI will be plotted versus study day per treatment, with all treatments overlain.

Logistic regression of the log odds of SRI response on log2 dose level (mg/kg) will be performed. Placebo subjects will be treated as a having dose of 0 mg/kg. Based on this model, the estimate of the slope and odds ratio (OR) for a doubling of dose will be presented with 95% CI (based on the profile likelihood) and two-sided p-value (Wald test).

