15.3.2.2. ANALYSIS

The analysis for BICLA response will replicate that performed for SRI.

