15.3.8.2. ANALYSIS

The analysis for incidence of flares will replicate that performed for SRI, and will be performed for each severity grade (mild/moderate and severe) and overall.

The flare-free survival function will be estimated by treatment group and for all active-treated subjects combined using Kaplan-Meier methodology, with 95% confidence intervals based on Greenwood's formula. These survival curves will be plotted. The KM estimates of quartiles for time to event with the corresponding 95% CIs will be provided for each treatment and for all active-treated subjects, when estimable, using Greenwood's formula.

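### The SRI dose-response model pairs a profile-likelihood CI with a Wald p-value and has no rule for separation, so the two can disagree, mainly for uncommon endpoints that copy the analysis

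*SAP*

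**What the plan says.** SAP 15.2.1.2 adds a dose-response model to the group comparisons for SRI: "Logistic regression of the log odds of SRI response on log2 dose level (mg/kg) will be performed". The slope and the odds ratio per doubling of dose "will be presented with 95% CI (based on the profile likelihood) and two-sided p-value (Wald test"). No alternative is given for the case where the maximum-likelihood estimate does not exist.

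The groups are small. Protocol 5.3 plans "8 subjects assigned to each of the 4 brentuximab vedotin dose cohorts and a total of 8 subjects assigned to placebo", and the Synopsis gives the levels: "The doses planned for each ascending dose cohort include 0.3, 0.6, 1.2, and 1.8 mg/kg". Extra cohorts recommended by the Safety Monitoring Committee could raise enrolment ("for a total of up to 60 subjects", SAP 3.1), but none is fixed in advance.

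The model is reused widely. SAP 15.3.2.2 says "The analysis for BICLA response will replicate that performed for SRI", and SAP 15.3.8.2 says "The analysis for incidence of flares will replicate that performed for SRI", for each severity grade and overall. BILAG response, SLEDAI response, ACR response, BILAG flares, renal flares, active renal disease and corticosteroid use are handled in the same way (SAP 15.3.1.2, 15.3.4.2, 15.3.7.2, 15.3.9.2 to 15.3.12.2).

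**The concern.** A 95% profile-likelihood interval is the set of slopes that a 5% likelihood-ratio (LR) test does not reject. It excludes an odds ratio of 1 exactly when the LR p-value is below 0.05. The Wald p-value instead divides the estimate by its standard error. In large samples the two agree. With 8 subjects per dose they need not, and one row of a table can show an interval that excludes 1 beside a non-significant p-value, with nothing in the SAP to say which governs.

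The extreme case is separation, where some dose cut-point divides responders from non-responders completely, or completely apart from ties at one dose. The fitted slope then runs off to infinity and its standard error grows faster, so the Wald p approaches 1.

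What is at stake is the reading of the only planned model that uses all doses together, for SRI and for each binary endpoint that copies it, in a study meant to inform the design of a larger one.

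**Working it through.** **Inputs.** Doses of 0.3, 0.6, 1.2 and 1.8 mg/kg with 8 subjects each (Protocol Synopsis and 5.3); covariate log2 dose, profile-likelihood CI and Wald p (SAP 15.2.1.2); nominal 5% level (Protocol 8.2). The documents give no SRI or flare rate, power or effect size, so there is no stated figure to reproduce, and every rate below is an assumption.

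**Method.** Each dose can have 0 to 8 responders, so the active doses have 9^4 = 6,561 possible tables. The model was fitted to every table, Wald and LR p-values were compared at 5%, and tables were weighted by their binomial probabilities. This is exact enumeration. Placebo was left out because its code is undefined (step 5).

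**1. Single tables** (responders of 8, lowest to highest dose).

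- 0, 0, 0, 4: separated. The best attainable log-likelihood is 8 ln(0.5) = -5.545. The null value is 4 ln(4/32) + 28 ln(28/32) = -12.057. LR = 2 x (12.057 - 5.545) = 13.02, p = 0.0003. Wald p = 0.9997. Firth's penalised LR test gives p = 0.004 with a finite odds ratio.
- 0, 0, 0, 1: separated, with weak evidence. The best log-likelihood is ln(1/8) + 7 ln(7/8) = -3.014 and the null is ln(1/32) + 31 ln(31/32) = -4.450. LR = 2.87, p = 0.09. Wald p is again near 1.
- 0, 1, 7, 8: not separated, with a very clear effect. Slope 4.167, SE 1.380, z = 3.02, Wald p = 0.0025; LR p = 1.5e-8.
- 1, 2, 5, 7: not separated. Slope 1.520, SE 0.527, z = 2.89, Wald p = 0.004; LR p = 0.0005.

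**2. Direction and size of disagreement.** No table has Wald p below 0.05 with LR p at or above it, so disagreement runs one way only. Without separation the largest Wald p beside an interval excluding 1 is 0.17, and the median over such tables is about 0.06. Separation occurs in 62 of the 6,561 tables.

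**3. How often (active doses only).**

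| Assumed rates at 0.3/0.6/1.2/1.8 mg/kg | CI excludes 1, Wald p >= 0.05 | Of which separated (Wald p near 1) |
|---|---|---|
| 30% at every dose | 2.6% | below 0.1% |
| 25/35/50/60% | 6.05% | 0.007% |
| 2/5/10/20% | 30% | 12% |
| 20/10/5/0% | 33% | 14% |

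Rates rising from 30% to between 50% and 80% give about 4% to 5%.

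**4. Error rate and power.** With one common rate of 10% to 40% at all doses, null rejection is 0.4-4.2% for Wald, 5.9-8.2% for unpenalised LR and 1.9-4.6% for Firth. Because the planned interval inverts the LR test, its null coverage is 100 - 8.2 = 91.8% to 100 - 5.9 = 94.1%. Power at 25/35/50/60% is 31% for Wald, 37% for LR and 32% for Firth. At 20/10/5/0% it is 6% for Wald and 15% for Firth.

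**5. With placebo.** The SAP also says "Placebo subjects will be treated as a having dose of 0 mg/kg", and log2(0) does not exist. With stand-in codes (log2(dose + 1), or placebo set at 0.15 mg/kg), disagreement over a range of assumed SRI rates is 0.7% to 6.0%. With placebo set at 0.01 mg/kg it is 2.0% to 11.3%. For rates rising from 2% to 20%, it is 25% to 36% across these codes.

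**The case against.** The strongest reply is that little depends on this p-value. There is no primary efficacy endpoint, testing is nominal and unadjusted, and escalation rests on safety review. Protocol 8.5.2 plans only proportions, intervals and Fisher's exact test. SAP 15.2.1.2 keeps Fisher's test of each dose against placebo and adds score-based intervals for the relative risk, all of which remain usable with sparse data. This stands, and it limits the importance of the point. It does not make the row coherent: Fisher's test compares one dose with placebo, 8 against 8, and does not test for a trend.

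Two stronger readings are tempting. A reader might infer that the interval and the p-value will contradict each other on SRI. At moderate rates they agree in about 94% of trials or more, and most disagreements look like p = 0.06 beside an interval that just excludes 1. A reader might also infer that the Wald p fails exactly when the dose effect is clearest. The tables 0, 1, 7, 8 and 0, 0, 0, 1 show otherwise: the cause is separation, not strength of evidence.

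It is also fair that a true rate of exactly 0% at one end makes separation more likely. The 2/5/10/20% row has no zero rate and still gives 30%. But that figure needs a dose trend as well as rarity: at a flat 5% rate, disagreement is only about 4% with placebo coded at 0.15 or 0.01 mg/kg.

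**Conclusion.** The point holds as a moderate one. The specified interval and p-value come from different tests, can disagree in one direction only, and have no fallback under separation. For SRI at assumed moderate rates the effect is small: about 2-6% of trials on active doses, mostly near misses. For uncommon endpoints with a dose trend it reaches about 30%, and in 12-14% of all such trials the Wald p is near 1 beside an interval that excludes 1. A row with p = 0.99 is therefore a realistic risk for rare flare or renal endpoints, not the expected outcome for SRI.

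These sizes rest on assumed event rates, 8 subjects analysed at each dose and, for the main figures, placebo left out. Whether flares will in fact be rare cannot be judged from the documents.

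**What to change.** In SAP 15.2.1.2, fit the model by Firth's penalised likelihood. Report its profile penalised-likelihood 95% CI with the matching penalised LR p-value, for SRI and every endpoint that replicates this section. State that the p-value is not taken from the Wald column, and that the full-model penalty is used in both fits, so that the test and the interval match.

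The change is one SAP sentence and one SAS option, plus a little programming for the p-value. The costs are that the odds ratio is shrunk toward 1 and that the test is conservative for rare events (null rejection as low as 1.9% within the range of common rates above).

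Do not simply replace the Wald p with the unpenalised LR p. That would match the planned interval, but it rejects in about 6-8% of null trials at common rates of 10% to 40% and leaves the odds ratio infinite under separation.

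Separately, define how placebo enters a log2-dose model. Until that is done the planned model cannot be fitted to all 40 subjects, whichever test is used.

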15.3. EXPLORATORY EFFICACY

All efficacy variables outside SRI are defined as exploratory for this protocol. All exploratory efficacy analyses will be performed using the FAS only. Analyses will be performed for all scheduled on-treatment assessments collected.

15.3.1. BILAG 2004

The BILAG disease activity index is assessed and scored by trained study investigators based the past 4 weeks of patient experience. Scoring is performed for each of the following domains: constitutional, mucocutaneous, central nervous system, musculoskeletal, cardiovascular/respiratory, abdominal, renal, ophthalmic and haematological. A total score will be derived from the nine domains by the investigator, as the maximum severity across the domains. No programmatic derivation is required for the index itself. BILAG scores are graded as follows: Grade A represents very active disease; Grade B represents moderate disease activity; Grade C

indicates mild stable disease; Grade D indicates no disease activity; Grade E indicates no current or previous disease activity.

No numeric scores will be assigned to the grades for any analyses.

15.3.1.1. DERIVATION

BILAG CLINICAL RESPONSE

BILAG Clinical Response is defined as:

- BILAG C scores or better in all organ domains; which includes by definition no new BILAG A or B scores in any organ domain

BILAG PARTIAL CLINICAL RESPONSE

BILAG Partial Clinical Response is defined as:

- at most 1 BILAG A or B score in any organ domain

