### **4.4 Selection of Study Population**

#### **4.4.1 Inclusion Criteria**

Subjects may be entered in the study only if they meet all of the following criteria:

1. Subject is able to provide written, informed consent.

2. Subject is an adult, aged  $\geq 18$  years.
3. Women of childbearing potential or male subjects with a WOCBP partner, will use 2 forms of highly-effective contraception method during the study through 6 months following the last dose of study drug. Women of childbearing potential includes any female who has experienced menarche and who has not undergone successful surgical sterilization (hysterectomy, bilateral tubal ligation, or bilateral oophorectomy) or is not postmenopausal. Postmenopausal is defined as amenorrhea  $\geq 12$  consecutive months without another cause, or documented follicle-stimulating hormone level  $> 35$  mIU/mL for women with irregular menstrual periods and on hormone replacement therapy (HRT). Acceptable forms of effective contraception include: established use of oral, injected, or implanted hormonal methods of contraception; placement of an intrauterine device or intrauterine system; barrier methods of contraception (condom or occlusive cap) with spermicidal foam/gel/film/cream/suppository; male sterilization; and true abstinence. Women of childbearing potential taking concomitant mycophenolate and oral contraceptives must use a barrier method of contraception along with their oral contraceptives.
4. If subject is a WOCBP, a serum pregnancy test result at screening and urine pregnancy test result at baseline must be negative.
5. Subjects must have a documented diagnosis of SLE for at least 6 months prior to screening according to both of the following:
  - a. fulfills at least 4 of 11 of the 1997 Update of the 1982 American College of Rheumatology (ACR) Revised Criteria for Classification of SLE; and
  - b. has a history of positive ANA ( $\geq 1:80$ ) or anti-dsDNA ( $\geq 30$  IU/mL) test prior to screening.
6. Subjects must have a positive ANA ( $\geq 1:80$ ) or anti-dsDNA ( $\geq 30$  IU/mL) test at screening (a single rescreening of previously positive subjects who were negative at screening will be allowed).
7. Subjects must demonstrate active SLE as indicated by a SLEDAI score  $\geq 4$  points at screening and at baseline.

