#### **6.2.3.3 Exploratory**

Exploratory efficacy outcomes include the following:

- proportion of subjects achieving a BICLA response at Day 85;
- proportion of subjects achieving a BILAG clinical response at Day 85
- proportion of subjects achieving a BILAG partial clinical response at Day 85, defined as BILAG C scores or better;

- proportion of subjects achieving a BILAG partial clinical response at Day 85, defined as a maximum of 1 BILAG B score or better;
- proportion of subjects achieving a SLEDAI clinical response at Day 85, defined by a  $\geq 4$  point improvement from baseline;
- proportion of subjects achieving organ-specific BILAG clinical response and partial clinical responses at Day 85 as determined by organ domain-specific scores;
- proportion of subjects achieving 20%, 50%, 70%, and n% (ACR20, ACR50, ACR70, and ACRn, respectively) improvement in SJC and TJC at Days 22, 43, 64, 85, 106, and 127;
- mean and median of observed and percentage change from baseline in SLEDAI, CLASI, TJC, SJC, PtGP, PtGA, PhGA, hsCRP, and ESR at Days 22, 43, 64, 85, 106, and 127;
- mean and median of observed and percentage change from baseline in organ domain-specific SLEDAI scores at Days 22, 43, 64, 85, 106, and 127;
- mean and median of observed and percentage change from baseline in HAQ-DI, SF-36, SF-36 Physical Component Summary (PCS), SF-36 Mental Component Summary (MCS), and FACIT-F at Days 43, 85, and 127;
- mean and median of observed and percentage change from baseline in urinary sediment (cellular casts, pyuria, hematuria), proteinuria (protein/creatinine ratio), and eGFR at Days 22, 43, 64, 85, 106, and 127; and
- mean and median of observed and percentage change from baseline in urinary sediment (cellular casts, pyuria, hematuria), proteinuria (protein/creatinine ratio), and eGFR at Days 22, 43, 64, 85, 106, and 127 in subjects with active renal disease at baseline.

Additional possible exploratory efficacy outcomes include the following:

- median time to treatment failure as defined by:
  - death or need for additional immunosuppressive therapy, or
  - death, end-stage renal disease, doubling of serum creatinine, or SLE or renal flare;
- incidence at Days 22, 43, 64, 85, 106, and 127 of SLE flares using the SELENA and BILAG definitions;
- median time to first mild/moderate and severe SLE flares using SELENA and BILAG definitions;
- incidence at Days 22, 43, 64, 85, 106, and 127 of renal flares;

- median time to first renal flare;

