15.3.1.2. ANALYSIS

BILAG domain scores will be tabulated by treatment group at each visit, plus categories for grade B or worse and grade C grade or better. Shifts from baseline among the grades will be tabulated similarly. Individual grades for each domain will be graphed over time, treating grade as ordinal, with one plot per subject.

The analysis for BILAG clinical response (full and partial) will replicate that performed for SRI.

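### The SAP's BILAG partial clinical response counts a subject with one A score and no B score as a responder; neither protocol definition admits an A.

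*SAP*

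**What the plan says.** Protocol 6.2.3.3 lists two exploratory endpoints called BILAG partial clinical response, both at Day 85. The first requires grade C or better. The second is "defined as a maximum of 1 BILAG B score or better".

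SAP 15.3.1.1 replaces these with a single rule: "at most 1 BILAG A or B score in any organ domain". It sets no condition relative to baseline.

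The grade order is in SAP 15.3.1: "Grade A represents very active disease", with B moderate, C mild and stable, D inactive and E never active. SAP 15.3.9.1 classes any new A domain score as a severe BILAG flare.

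On the analysis, SAP 15.3.1.2 states: "The analysis for BILAG clinical response (full and partial) will replicate that performed for SRI". The SRI analysis in SAP 15.2.1.2 consists of response percentages with Wilson intervals, Fisher's exact test of each dose against placebo, and a logistic regression on log2 dose. It also specifies: "The ratio of percentages (relative risk) for active to placebo will be presented for each dose level".

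SAP 3.4 reports no meaningful departure from the protocol's planned analyses.

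**The concern.** The SAP rule is the one that will be programmed, and it puts the most severe grade on the responder side of the table. A subject who enters with a single A and no B, and does not change, is a partial responder. So is a subject whose only A or B score is a newly developed A. At that visit the SAP would count the same subject as a severe flare under 15.3.9.1 and as a partial responder under 15.3.1.1. The other composite responses in the SAP, SRI (15.2.1.1) and BICLA (15.3.2.1), both bar new A scores.

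With 8 subjects per dose and 8 on placebo, a single reclassified subject visibly moves the reported percentage and relative risk. The trial is meant to inform the design of a larger efficacy study, so a responder rate that includes unimproved or worsened disease could mislead even without formal inference. A reader relying on SAP 3.4 would not know that the definition had changed.

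**Working it through.** **1. The rules side by side.** Let a and b be the numbers of domains graded A and B, out of the nine BILAG domains.

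| Rule | Condition | One A, no B |
|---|---|---|
| Protocol 6.2.3.3, first definition | a + b = 0 | non-responder |
| Protocol 6.2.3.3, second definition | a = 0 and b ≤ 1 | non-responder |
| SAP 15.3.1.1 | a + b ≤ 1 | responder |

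The second row takes better than B to mean C, D or E, which follows from the grade order in SAP 15.3.1.

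**2. What the SAP adds.** Count grade profiles with five grades in nine domains. These are possible profiles, not patient frequencies.

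- No A and no B: 3^9 = 19,683.
- Exactly one B and no A: 9 × 3^8 = 59,049. The second protocol definition therefore admits 19,683 + 59,049 = 78,732.
- Exactly one A and no B: 9 × 3^8 = 59,049. The SAP rule therefore admits 78,732 + 59,049 = 137,781.

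Every profile that the SAP admits and the second protocol definition does not has exactly one A and no B. A full listing of all 5^9 profiles gave the same counts with no exceptions.

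**3. Effect on a percentage.** Planned sizes are 8 per dose and 8 pooled placebo (Protocol 4.1). One reclassified subject adds 100/8 = 12.5 points with all 8 in the denominator.

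**4. Effect on the relative risk.** Suppose an arm has k true responders and gains one, with denominators unchanged.

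- Gain on placebo: the relative risk is multiplied by k/(k + 1), which is 0.50, 0.67 or 0.75 for k = 1, 2 or 3.
- Gain on active: it is multiplied by (k + 1)/k, which is 2.0, 1.5 or 1.33 for k = 1, 2 or 3.

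Illustration: 4/8 against 1/8 gives a relative risk of 4.0, a difference of 37.5 points and two-sided Fisher p = 0.28. One added placebo responder gives 4/8 against 2/8: relative risk 2.0, difference 25 points, p = 0.61.

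**5. Effect on the nominal test.** Take every 8-against-8 table with 0 to 8 active and 0 to 7 placebo responders: 9 × 8 = 72. Adding one placebo responder moves Fisher's p across 0.05 in 8 of them. In 4 of these an apparent drug benefit is lost (starting from 5 v 0, 6 v 1, 7 v 2 or 8 v 3). In the other 4 placebo was already ahead. This is an unweighted count of tables, not a probability.

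**The case against.** The best defence is that little depends on this. The endpoint is exploratory, p-values are nominal, and SAP 7.4 calls the study hypothesis-generating. SAP 15.3.1.2 also tabulates each domain's grades, gives shift tables and plots every subject, so A scores remain visible. Exclusion Criterion 9 removes urgent, severe disease needing immediate immunosuppression, and Protocol 4.4.4 withdraws subjects whose worsening warrants a significant change in therapy. Both may reduce the number with an A at Day 85. All of this stands and limits the importance. It does not make the responder table right: neither provision bars an A, and the inclusion criteria set a SLEDAI minimum but no BILAG condition.

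The protocol text is also imperfect. It does not print the words no A; that follows from the grade order. Its C-or-better definition, read across all domains, duplicates full response. This supports clarifying the definitions, but no reading of the protocol lets an A in.

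A reader might infer more than the documents support:

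- **That the error repeats at six visits.** The protocol sets this endpoint at Day 85 only. SAP 15.3 limits exploratory analyses to on-treatment assessments while 15.3.1.2 copies the SRI analysis, so whether Days 106 and 127 are included is unclear.
- **That each subject adds more than 12.5 points because denominators shrink.** SAP 15.1 uses available data but also treats assessments missed during participation as non-events, so a larger step would require subjects to have left the study.
- **That the rule makes every subject an organ-specific responder.** The SAP does not say that the rule applies to single domains.
- **That the category pooling B or worse is a second error.** It is shown in addition to the individual grades.

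**Conclusion.** The SAP rule is wrong as written against the protocol: it classifies one A with no B as partial response, conflicts with the SAP's own severe-flare definition when that A is new, and is not declared in SAP 3.4. The conclusion rests only on the two definitions and the grade order.

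The size is known per subject, not overall. Each affected subject adds 12.5 points to an arm of 8 with a full denominator. The relative risk can halve or double when the affected arm has one true responder. The direction depends on which arm the subject is in, so the documents do not support a claim of bias towards the drug. The nominal Fisher result would usually stay on the same side of 0.05. The consequence is confined to one exploratory endpoint; SRI and the safety objective are unaffected. It should be corrected, but it does not threaten the trial's main conclusions.

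**What to change.** In SAP 15.3.1.1, define BILAG partial clinical response as no A score and at most one B score across all domains, consistent with the second definition in Protocol 6.2.3.3. State whether the protocol's C-or-better version is kept as a second definition or is dropped because it duplicates full response. If the sponsor does intend to admit a single A, say so in SAP 3.4 and give the reason.

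The cost is a few lines of SAP text and the matching line of derivation code, to be settled before database lock and unblinding. Data collection, sample size and analysis sets do not change.
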